Using a chi-square test and setting alpha at 0.05, the probability of detecting a statistically significant difference in the proportion of children with symptoms of any FGID with improvement in the primary outcome at 3 months from baseline between the intervention and the control group is 90%, with an effective sample size of 163 per group. Hence, the total effective sample size (n\*) is 326.

The unit of randomization is the clinic, but the unit of analysis is the individual patient. Since patients are nested within practice, responses from the patients within practice are likely to be

correlated. This intra-cluster correlation must be taken into account in the calculation of sample size and in the analyses. We computed the number of patients per clinic,  $m$ , required for the study, using the following equation:

$$m = \frac{1 - \rho}{\frac{k}{n^*} - \rho}$$

where  $\rho$  = intra-practice correlation  
 $k$  = number of clinics  
 $mk$  = total sample size  
 $n^*$  = total effective sample size =  $mk/DE$   
and  $DE$  = design effect =  $1 + \rho(m-1)$

Using 6 clinics and assuming intra-class correlation of 0.014, we need to recruit 224 families with a child between 0 and 18 per clinic. We anticipate that drop-out is not a major problem and unlikely to be more than 10% for the primary outcome. We will account for this factor by oversampling patients by 10%. According to the data presented in Table 3 and with an assumption that for each category of FGID diagnosis 50% of the patients will be in the control clinics and other 50% will be in intervention clinics, there will be about 5,500 patients/year/group with a FGID diagnosis. If we assume that only 66% of the parents will respond to the phone call at 3-month post baseline, we will have 3,630 patients/year/group. Therefore, the number of patients from which we are able to recruit is not a factor at all. We can have more than 90% power even to detect a 5% absolute difference with all available patients in one year.

**Data Analysis.** Baseline clinical and demographic data will be compared between the intervention and the control groups. Categorical variables will be examined using chi-square tests and continuous measures with Student's t-tests. The statistical analysis of the data will be performed using the SAS.

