**Primary Outcome Analysis:** The primary outcome is whether there was resolution of symptoms of a FGID by Rome IV criteria in children and adolescents or whether parental reassurance was achieved for infants. For this dichotomous outcome, we will use a non-linear mixed-effects model and will adjust for potential confounders (fixed effects) and clinic effects (random effects). To be specific, if  $Y_{ik}$  is a binary variable indicating whether the  $k^{\text{th}}$  patient in the  $i^{\text{th}}$  clinic was reported a resolution of FGID symptom, we have

$$\text{logit}(Y_{ik} = 1) = \alpha_i + \mathbf{X}_{ik}\beta, \text{ where } \alpha_i \sim N(0, \sigma^2).$$

The random component  $\alpha_i$  correlates outcomes of patients cared by the same clinic. Physicians would not be considered as a nesting factor since the same patients at different visits may not be seen by the same physician. The vector  $\mathbf{X}_{ik}$  represents fixed covariates and  $\beta$  represents the corresponding coefficients. The fixed covariates will include critical covariates such as treatment group, gender, and other patient and clinic level characteristics. We will also examine potential interaction terms among the covariates, particularly interactions between treatment arm and other covariates. If there is a significant treatment difference, we will report the 95% confidence interval of the treatment difference after adjusting for all confounding factors. The model will be fitted by the SAS procedure NL MIXED.

**Secondary Outcome Analyses:** The additional time points of 1, 6, and 12 months will be modeled identically to the primary outcome analysis. Furthermore, we will have a number of secondary outcomes which are count data aggregated within the 12 months after initial Rome IV

diagnosis. We will use Poisson regression to model these count data. To adjust for the possible differences between the intervention and control groups, we will use an approach similar to the analyses of primary outcomes and again clinic will be considered as a cluster factor to take into consideration the correlation in count data within each clinic. Family and provider satisfaction scores will be analyzed using Student's t-test, as well as a linear mixed-effects model as with other outcomes.

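### Baseline comparisons, and one of two planned satisfaction analyses, ignore clinic although the SAP says clustering must enter the analyses; at its own ICCs a nominal 5% test would reject about 22% to 33% of the time with 224 per clinic

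*SAP*

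**What the plan says.** The SAP's Sample Size and Power Estimates section sets out the design: "The unit of randomization is the clinic, but the unit of analysis is the individual patient". It expects patients in the same practice to respond alike, and draws the rule: "This intra-cluster correlation must be taken into account in the calculation of sample size and in the analyses".

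The Data Analysis paragraph that follows says "Baseline clinical and demographic data will be compared between the intervention and the control groups". It then gives the method: "Categorical variables will be examined using chi-square tests and continuous measures" by Student's t-test. No clinic term, cluster adjustment or clinic-level summary is mentioned there.

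Under Primary Outcome Analysis, the dichotomous outcome is modelled with a random clinic effect. The fixed covariates are treatment group, gender and an unlisted set of further patient-level and clinic-level characteristics. Under Secondary Outcome Analyses, the other time points follow the same model and the count outcomes treat clinic as a cluster factor. For satisfaction the text is: "Family and provider satisfaction scores will be analyzed using Student's t-test, as well as a linear mixed-effects model as with other outcomes". It does not say which of the two results is the reported one.

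**The concern.** Chi-square tests and Student's t-tests take every patient as independent. When whole clinics are allocated, the variance of a difference between arms also contains the variation between clinics. A test that leaves this out uses too small a standard error and rejects too often. The SAP states this principle and applies it to the primary, repeated time-point and count outcomes. The baseline tests and the satisfaction t-test are the exceptions.

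Two things are at stake. For satisfaction, the plan as written allows a p-value with the wrong error rate to be reported as a trial result, next to or instead of the one from the mixed model. For baseline data, the p-values would make chance differences between two small sets of clinics look like stronger evidence against chance allocation than they are. The list of confounders for the primary model is open, and nothing in the SAP stops such p-values from influencing it.

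**Working it through.** **Inputs**

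- Clinics, ICC and patients per clinic, from Sample Size and Power Estimates: "Using 6 clinics and assuming intra-class correlation of 0.014, we need to recruit 224 families" per clinic. So k = 6, ρ = 0.014, m = 224.
- Total effective sample size n* = 326, same section.
- ICC the SAP estimated before doubling it for caution: 0.007, same section. Both ICCs were derived for the primary outcome.
- Test level: "Using a chi-square test and setting alpha at 0.05". Sidedness is not stated; two-sided is assumed.
- Survey maximum in the protocol (section B, description of research interactions): 600 participants. Spread evenly, 600/6 = 100 per clinic.
- Three clinics per arm, all of equal size: an assumption. The SAP assumes only a 50:50 split of patients.

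**Step 1: reproduce the SAP's figure.** m = (1 − ρ)/(k/n* − ρ) = (1 − 0.014)/(6/326 − 0.014) = 223.84, so 224. The SAP's number is recovered.

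**Step 2: true size of an unadjusted test.** The SAP gives no such figure. Its own design effect is DE = 1 + ρ(m − 1). The unadjusted test statistic has variance of about DE instead of 1 under the null, so the true size is 2[1 − Φ(1.96/√DE)].

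For m = 224 and ρ = 0.014: DE = 1 + 0.014 × 223 = 4.122, √DE = 2.030, 1.96/2.030 = 0.965, true size 33.4%.

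| m per clinic | ρ | DE | True size of a nominal 5% test |
|---|---|---|---|
| 224 | 0.014 | 4.122 | 33.4% |
| 224 | 0.007 | 2.561 | 22.1% |
| 100 | 0.014 | 2.386 | 20.5% |
| 100 | 0.007 | 1.693 | 13.2% |

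With the SAP's 10% oversampling (224 × 1.1, about 246 per clinic) the values are 35.2% and 23.4%.

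**Step 3: check by simulation.** In 40,000 simulated null trials with three clinics per arm, m = 224 and ρ = 0.014, the pooled t-test on normal data rejected in 33.7%. The chi-square test on beta-binomial data with mean 0.30 rejected in 33.8%. At m = 100 and ρ = 0.007 the rates were 13.1% and 13.4%. A t-test on the six clinic means (4 degrees of freedom) rejected in 5.0% at m = 224 in the normal data. This shows that the excess comes from leaving clinic out. It does not test how the planned mixed model behaves with six clinics.

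**Step 4: sensitivity to the ICC.** At m = 224, an assumed ICC of 0.001 gives 7.6% and an assumed 0.05 gives 57.4%. The range in the table is therefore conditional on the SAP's two values and bounds the truth in neither direction.

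**The case against.** The strongest reply is that every outcome in the SAP already has an analysis that includes clinic. The sentence before the clustering rule speaks of patients' responses, and baseline characteristics are not clearly responses. Baseline tests are descriptive. With six clinics, an imbalance among enrolled patients is a real difference, and adjusting for a prognostic one can be sensible. The ICCs in the calculation belong to another variable, and 0.014 was deliberately doubled.

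Much of this stands, and it rules out several stronger readings:

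- A reader might infer that satisfaction is analysed without regard to clinic. It is not: a linear mixed-effects model is planned, and no chi-square test is planned for satisfaction. The defect is the extra t-test and the missing order of precedence.
- A reader might take one in three as the general false-positive rate. It holds only at 224 per clinic and ICC 0.014.
- A reader might call the computed rates a floor, on the ground that demographic variables cluster more than outcomes. The documents give no ICC for any such variable.
- A reader might infer that covariates will be picked from the baseline tests, or that the primary type I error is inflated. The SAP does not say the former, and the primary model has its random clinic effect. The open covariate list is a prespecification gap that would remain without these tests.

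What does not stand is the defence of the satisfaction t-test. Satisfaction is an outcome, the t-test is a stated between-arm analysis, and its error rate is wrong under this design. For baseline data, reading the rule narrowly does not make the p-values valid; it only makes the inconsistency less explicit.

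**Conclusion.** The point holds in limited form. The baseline chi-square and t-tests and the satisfaction t-test leave out clinic, at odds with the SAP's own rule. If the primary-outcome ICCs of 0.007 to 0.014 are assumed for these variables, a nominal 5% test has a true size of about 22% to 33% at 224 per clinic and about 13% to 20% at 100 per clinic. This also assumes equal clinic sizes, three clinics per arm and two-sided testing.

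The figures can be read for patient-level baseline variables and, under the same assumption, for family satisfaction. They cannot be carried over to provider satisfaction, which is measured on providers, whose number per clinic is not given.

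The primary model's random clinic effect is not affected. The consequences are a satisfaction p-value that may be invalid, and baseline p-values that overstate imbalance and could, with nothing to prevent it, influence the choice of confounders.

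**What to change.** - Secondary Outcome Analyses: delete the Student's t-test for satisfaction and name the linear mixed-effects model with a clinic effect as the only analysis of these scores.
- Data Analysis: summarise baseline data by arm and by clinic without p-values. If tests are wanted, use ones that account for clinic; either choice would satisfy the SAP's own rule.
- Primary Outcome Analysis: state that covariates are not chosen from the baseline comparisons.

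The cost is a few sentences in the SAP. No new data, patients or procedures are needed, and the replacement for satisfaction is a model already planned.

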Systematic Pediatric Assessment of Rome Criteria (SPARC)

Principal Investigator: [name] MD

IRB Protocol # 1811325201

NCT04773158

April 1, 2019

**Sample Size and Power Estimates.** We calculated our sample size using the binary primary outcome (whether there was resolution of symptoms of a FGID by Rome IV criteria in children and adolescents or whether parental reassurance was achieved for infants). We wish to detect a 15% difference between the control and intervention clinics in the rate of the primary outcome. Since each FGID has a different estimated background rate of improvement without intervention, we estimated an overall weighted average improvement rate. We also took into consideration of differences of prevalence of different FGID diagnosis. Therefore, based on the data presented in Table 3, we estimated an overall improvement rate of 30% for the control clinics. Though we do not anticipate much variability in this rate at our six study clinics, we will use six different rates in a wide range, 15%, 20%, 25%, 30%, 35% and 40%, at baseline in order to estimate intra-clinic correlation. This translates to an intra-class correlation coefficient 0.007. However, for a conservative estimation of sample size, we will use intra-class correlation 0.014, two times the intra-class correlation we estimated.

Table 3. Data Utilized for Sample Size Calculations				
FGID Diagnosis	Estimated Baseline Improvement in 3 months	Prevalence	Unique CHICA patients/yr in age group	Minimum Time Required
Infant regurgitation (0-12m)	25%	10%	3172	10 months
Infant dyschezia (0-9m)	25%	5%	2640	26 months
Infant colic (0-5m)	48% 	10%	1584	26 months
Cyclic vomiting syndrome (3m-18y)	70% 	5%	22544	4 months
Functional nausea/vomiting (8-18y)	50%	5%	9702	8 months
Functional dyspepsia (8-18y)	25%	10%	9702	4 months
Irritable bowel syndrome (8-18y)	37.5% 	15% 	9702	4 months
Abdominal migraine (8-18y)	20%	2% 	9702	16 months
Functional abdominal pain - NOS	20%	15%	9702	4 months
Functional constipation (0-18y)	20%	20%	23336	3 months

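### Unnamed clinic-level covariates in the primary model use up the four between-clinic degrees of freedom that six clinics leave: a valid test loses power, or an uncorrected test over-rejects more

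*SAP*

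**What the plan says.** The SAP, under Sample Size and Power Estimates, states: "The unit of randomization is the clinic, but the unit of analysis is the individual patient". The protocol's research-design section likewise places randomization at the clinic site. The same SAP section sizes the trial "Using 6 clinics and assuming intra-class correlation of 0.014" and arrives at 224 families per clinic.

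Under Primary Outcome Analysis, the binary outcome is modelled by logistic regression with a random clinic intercept, fitted in the SAS procedure for non-linear mixed models. On the fixed part it says: "The fixed covariates will include critical covariates such as treatment group, gender, and other patient and clinic level characteristics". It adds: "We will also examine potential interaction terms among the covariates, particularly interactions between treatment arm and other covariates".

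The SAP does not list or count the clinic-level characteristics. It also gives no reference distribution, degrees of freedom or small-sample correction for the treatment test.

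**The concern.** Treatment varies only between clinics, so the evidence on it is limited by the number of clinics, however many patients each one contributes. Each clinic-level covariate in the primary model does two things. It removes one of four degrees of freedom, and it is correlated by chance with the allocation, which inflates the variance of the treatment estimate. Four such covariates would leave nothing from which to estimate clinic variation.

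A single covariate can be enough to break the model. If a yes/no characteristic splits the clinics three and three, there are C(6,3) = 20 possible splits, and 2 of them coincide with a 3 v 3 allocation. With probability 2/20 = 10% it cannot be separated from treatment at all.

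The primary conclusion is at stake, because an open list lets the choice of clinic characteristics move the treatment estimate. A treatment-by-covariate interaction, if one were kept, would turn the treatment coefficient into an effect at one covariate level.

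**Working it through.** **Inputs from the SAP.** Six clinics; 224 patients per clinic; intra-class correlation ρ = 0.014; control rate ("we estimated an overall improvement rate of 30% for the control clinics"); effect ("We wish to detect a 15% difference between the control and intervention clinics in the rate of the primary outcome"). The protocol's hypothesis is improved resolution, so the comparison is 30% v 45%.

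**Assumptions.** Three clinics per arm (the SAP gives only a 50/50 split of patients), equal clinic sizes, two-sided 5%.

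**The plan's own figures.** Patients per clinic: m = (1 − ρ)/(k/n* − ρ) = 0.986/(6/326 − 0.014) = 223.8, so 224 reproduces. The design effect is 1 + 0.014 × 223 = 4.12, and 1,344/4.12 ≈ 326 effective, or 163 per group.

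The power does not reproduce. The SAP says "Using a chi-square test and setting alpha at 0.05" power "is 90%, with an effective sample size of 163 per group". For 30% v 45%, 163 per group gives 80.2%, and 90% needs 217. About 90% appears only for 30% v 15%, a fall in resolution. The figures below therefore start from the recomputed 80%.

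**Valid test, no clinic-level covariate.** Noncentrality = 0.15/√[(0.30 × 0.70 + 0.45 × 0.55)/163] = 0.15/√(0.4575/163) = 2.83. On 4 degrees of freedom (critical t 2.78) power is 57%.

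**Loss of degrees of freedom alone** (covariates orthogonal to arm and unrelated to outcome). With one covariate, 3 degrees of freedom (critical t 3.18) give 49%. With two, 2 degrees of freedom (critical t 4.30) give 36%.

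**Adding chance correlation with arm.** Trials were simulated with 6 clinics × 224 patients and 20,000 to 40,000 runs per setting. Covariates were unrelated to outcome. The valid test is a t-test on clinic proportions with 4 − q degrees of freedom. The uncorrected test uses a maximum-likelihood-type variance, referred either to an assumed t(5) or to z.

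| Clinic covariates (q) | Valid t: null / power | Uncorrected, t(5): null / power | Uncorrected, z: null / power |
|---|---|---|---|
| 0 | 5% / 57% | 8% / 76% | 16% / 87% |
| 1 | 5% / 41% | 11% / 73% | 21% / 84% |
| 2 | 5% / 24–25% | 15% / 69% | 26% / 79% |
| 3 | 5% / 11% | 18% / 61% | 31% / 71% |

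A direct random-intercept logistic fit with no clinic covariate (1,500 trials) rejected the null in 9% (t(5)) and 17% (z), close to the first row.

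**Prognostic covariates, valid test.** One covariate explaining 50% of between-clinic variance gives about 57%, which is break-even; one explaining 90% gives about 81%. Two together explaining 50%, 80% or 90% give about 34%, 45% or 52%.

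**Sensitivity to clinic size.** With 202 or 249 per clinic instead of 224, power on 4 degrees of freedom is 56% or 58%. Even with unlimited patients, effective size is capped at k/ρ = 6/0.014 = 429 in total, or 214 per group. At 217 per group, just above that cap, the figures would be 69% with no clinic covariate and 30–44% with two.

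**The case against.** Five points can be made for the plan.

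- **The SAP proposes a mixed logistic model, not a t-test on clinic proportions.** On the uncorrected version, nominal power with two covariates is still about 69–79%. This stands as a description, but that power comes with a false-positive rate of 15–26%.
- **The SAP never says two.** The plural may cover patient and clinic characteristics together. This stands: two is only an illustration. The absence of any number or limit is itself part of the problem.
- **The covariates are meant as confounders, so treating them as noise is the least favourable case.** This stands in part. One strong predictor, named in advance, is defensible and could raise power. With two, even 90% of between-clinic variance explained leaves power just under the 57% available without them, and the SAP identifies no such predictor.
- **Over-rejection is present with no clinic covariate at all** (8% or 16%). This stands. Removing the covariates removes only the increment, so the fix must also set the degrees of freedom.
- **Interactions are only to be examined.** This stands. The SAP does not say that one would stay in the primary model, so that harm is conditional and has not been sized.

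A reader might infer that the plan both cuts power to about 25% and inflates type I error. The documents do not support that. The two harms belong to different tests: the one that loses power this way holds type I error at 5%, and the one that over-rejects keeps most of its nominal power. Because the SAP does not say which test applies, it is exposed to one or the other. Nor is 25% a figure that the plan implies; it is the low end of about 25–52% for an assumed two covariates.

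**Conclusion.** The concern holds as an open-ended specification that worsens the primary test. With six clinics, every clinic-level covariate costs a degree of freedom that the sample-size calculation, a chi-square test with a design effect, never budgeted for. The consequence depends on how the treatment test is carried out. With degrees of freedom respected, covariates unrelated to outcome reduce power by roughly 8 to 16 points for one (57% to 49% or 41%) and 21 to 32 points for two (57% to 36% or 25%). With degrees of freedom ignored, two covariates add roughly 7 points (t(5)) or 10 points (z) to a type I error already above 5%.

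These sizes rest on a 3 v 3 allocation, equal clinics and the SAP's own intra-class correlation. They also rest on an assumed number of covariates, and the t(5) reference is assumed because the SAP names none. The direction does not depend on these choices, except that one covariate explaining more than about half of the between-clinic variance would help a valid test.

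**What to change.** Replace the sentence on fixed covariates with wording to this effect: the primary model contains treatment group and a listed, pre-specified set of patient-level covariates; no clinic-level covariate and no interaction enters the primary test; the treatment effect is tested on between-clinic degrees of freedom (6 − 2 = 4) or by an equivalent small-sample method, named in the SAP.

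Show clinic-level characteristics by arm in a descriptive table, and adjust for them one at a time in sensitivity analyses. Report treatment-by-covariate interactions as exploratory estimates with confidence intervals. Make the change before outcomes are examined by arm.

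The cost is SAP wording only: no new data, clinics or patients. There are two downsides. A strong clinic-level predictor would be adjusted for only in a sensitivity analysis. The power statement would also have to come down, to about 57% on the SAP's inputs with 30% v 45%, in place of the stated 90%.

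### The SAP commits to a 95% confidence interval for the primary effect only in the event of significance, so a non-significant result has no committed measure of which effects it excludes

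*SAP*

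**What the plan says.** The SAP's Primary Outcome Analysis section fits a logistic model with clinic as a random effect: "we will use a non-linear mixed-effects model and will adjust for potential confounders (fixed effects) and clinic effects (random effects"). It then sets out what will be reported: "If there is a significant treatment difference, we will report the 95% confidence interval", the interval being for the confounder-adjusted treatment difference. The scale of that difference (odds ratio, risk difference or other) is not named.

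This is the only confidence interval mentioned in the SAP or the protocol. No section commits to a point estimate or an interval for a primary comparison that is not significant.

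The Secondary Outcome Analyses section applies the primary model unchanged at 1, 6 and 12 months. It uses Poisson regression with clinic as a cluster factor for the 12-month counts, and t-tests plus a linear mixed model for satisfaction scores. It contains no interval rule of its own.

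**The concern.** A p-value above 0.05 does not show which effects the data are compatible with. The trial is built around one target: "We wish to detect a 15% difference between the control and intervention clinics in the rate of the primary outcome". After a non-significant result, the useful question is whether a 15-point benefit has been ruled out or remains plausible, and only the interval answers that.

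The plan secures the interval in the branch where it is needed less, and leaves it to later choice in the branch where it is needed more. With six clinics as the randomised units, the second branch is a realistic prospect even if the module works as hoped. The same gap extends to the other time points, and the count and score outcomes have no commitment either.

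**Working it through.** **Inputs**

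- Control rate: "we estimated an overall improvement rate of 30% for the control clinics" (SAP, Sample Size and Power Estimates).
- Target: 15 points. The protocol's statement of purpose hypothesises better resolution with the intervention, so the comparison is 30% v 45%.
- Test: "Using a chi-square test and setting alpha at 0.05". Sidedness is not stated; two-sided is assumed.
- Power and size: "between the intervention and the control group is 90%, with an effective sample size of 163 per group".
- Six clinics, intra-class correlation (ICC) 0.014, 224 families per clinic. The SAP's own ICC estimate before doubling is 0.007.
- Protocol, description of research interactions: at most 600 parents and older patients surveyed.
- My assumptions: three clinics per arm, and, for the small-sample version, 6 - 2 = 4 between-clinic degrees of freedom. The SAP states none.

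**1. Reproduce the plan's figures**

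The cluster step reproduces: m = (1 - 0.014)/(6/326 - 0.014) = 223.8, rounded to 224. The design effect is 1 + 0.014 × 223 = 4.122, and 6 × 224/4.122 = 326.

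The chi-square step does not. With mean rate 0.375,

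n = [1.960 √(2 × 0.375 × 0.625) + z √(0.21 + 0.2475)]² / 0.15².

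This gives 163 per group at 80% power and 217 at 90%. Power at 163 is 80.2%, not 90%. That is a separate matter, but it means the non-significant branch has about twice the probability the SAP implies (20% rather than 10%) before any small-cluster allowance.

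**2. Precision at 163 per group**

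SE = √[(0.30 × 0.70 + 0.45 × 0.55)/163] = √(0.4575/163) = 0.0530, or 5.3 points.

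- Normal half-width: 1.96 × 5.30 = 10.4 points.
- 4 df half-width: 2.776 × 5.30 = 14.7 points.

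**3. Chance of a non-significant result if the 15-point effect is real**

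The standardised effect is 0.15/0.0530 = 2.83.

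- Normal: Φ(1.96 - 2.83) = 0.19.
- Noncentral t, 4 df: 0.43 (with 5 df, 0.38).

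**4. Sensitivity to the inputs**

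| Assumption | Effective n per group | Normal | 4 df |
|---|---|---|---|
| ICC 0.007, 224 per clinic: 672/(1 + 0.007 × 223) = 672/2.561 | 262 | 5% | 23% |
| ICC 0.014, 224 per clinic (SAP) | 163 | 19% | 43% |
| ICC 0.014, 600 surveyed, 100 per clinic: 300/(1 + 0.014 × 99) = 300/2.386 | 126 | 30% | 53% |

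The last row takes the cap as 600 children, split evenly over the clinics.

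**5. What a non-significant result could mean**

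The control rate is 30%, with 163 per group. Intervals are unadjusted risk differences, d ± quantile × √{[0.21 + (0.30 + d)(0.70 - d)]/163}.

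| Observed difference (points) | 95% CI, normal | Excludes 15? | 95% CI, 4 df | Excludes 15? |
|---|---|---|---|---|
| 0 | -9.9 to +9.9 | Yes | -14.1 to +14.1 | Yes, narrowly |
| +5 | -5.2 to +15.2 | No | -9.4 to +19.4 | No |
| +10 (z = 1.89) | -0.3 to +20.3 | No | -4.6 to +24.6 | No |

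All three would be declared non-significant, yet their implications for the target effect differ.

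**The case against.** A reader might infer that the SAP forbids an interval after a null result, or that none would be reported. The text does not go that far. It says *if*, not *only if*: it makes a commitment in one case and is silent on the other. The authors may well intend to report the interval throughout, and the fitted model yields the treatment coefficient whatever the p-value. What stands is that a pre-specified plan counts for what it commits to, and here the commitment covers one branch only. If the interval was always meant to appear, the condition serves no purpose.

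A reader might also infer that a non-significant result is likely even with a real 15-point effect. The figures do not support that as a general statement. Under the SAP's own sample-size inputs the chance is below one half with either quantile. It passes one half only when the 600-survey cap and 4 df are combined, and both the even split and the df are assumptions. At the SAP's undoubled ICC with normal quantiles it is about 5%.

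It can fairly be said that this is a reporting sentence, with no effect on data, model, test or error rate. That is correct and sets the weight of the point. It is also true that estimates selected for significance tend to be too large, but reporting every interval does not undo that selection, so the case for the change does not rest on it.

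**Conclusion.** The concern holds as a gap in commitment: the SAP promises the primary interval only in the event of significance, and nothing in either document covers the alternative. This rests on the text, not on any calculation.

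The calculations show that the gap has practical weight. The uncovered branch has a probability of about 19% (normal) to 43% (4 df assumed) at the SAP's effective size under the target effect, and about 5% to 53% over the wider range of inputs. Results within that branch can either exclude the 15-point target or leave it open.

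The figures assume a two-sided 0.05 test, 30% v 45%, equal arms, and unadjusted risk differences standing in for an adjusted logistic model whose interval scale the SAP does not name. The point is a free improvement, not a flaw that invalidates the design.

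**What to change.** Delete the condition in the Primary Outcome Analysis section and replace the sentence with:

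> The adjusted treatment effect and its 95% confidence interval will be reported for the primary and each secondary outcome regardless of the p-value, on the scale of that outcome's model (odds ratio for binary outcomes, rate ratio for counts, mean difference for scores).

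Naming the scale by outcome matters, because odds ratios and risk differences do not fit the Poisson counts or the satisfaction scores.

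A risk difference for the primary outcome would be easier to set against the 15-point target, but it is not a coefficient of the random-intercept logistic model. It is optional. If wanted, the SAP should state how it will be standardised from the model and how its variance will be obtained.

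Cost: one sentence in the SAP, with no change to data collection, sample size or model. The optional risk difference adds a short method statement and some programming.
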